- c. A covariate adaptive randomization process will be used, balancing groups based on race (white vs. non-white); anxiety/depressive symptomology (high vs. moderate); and gender identity (cis-male vs. non-binary) if sample size allows for this.

4) Care Packages:

- a. Prior to the start of the interventions, all participants (intervention and control) will be sent a study care package, which will contain a yoga mat, condoms, lubricant, raisins, pen, journal, stickers, and a fidget spinner / stress ball, along with a brief description and purpose for each of the items.

Weekly Assessments, Post-Intervention and Follow-up Procedures

1) *Weekly Assessments:* During the 10-week intervention period, participants will be sent invites (via Qualtrics- individualized links) to complete weekly assessments designed to capture: (a) monitoring of sexual risk (condomless sex); (b) monitoring of depression (PHQ-9) and anxiety symptoms (GAD-7); and (c) self-report of weekly/daily practice time spent on intervention. Participants will be compensated \$5 per each weekly assessment completed (up to \$50 total).

2) *Post-Intervention Assessment:*

- a. Similar to the baseline survey, participants will be asked to complete a post-intervention assessment via Qualtrics. The assessment is estimated

to take 60 minutes to complete, and participants will be compensated \$30 for their time.

- b. Cortisol genetic testing kits and STI/HIV self-tests will be mailed out to participants post-intervention. Participants will be compensated \$20 for each completed test (\$40 total).

3) *Exit Interviews (Intervention Group Only):*

- a. Semi-structured interviews with intervention group participants will be conducted one-on-one via Zoom post-intervention to gather qualitative feedback on the study intervention.
- b. Interviews are estimated to take 90-120 minutes.
- c. Participants will be compensated \$40 for their time.

4) *6-month Follow Up Assessment:*

- a. Similar to the baseline and post-intervention surveys, participants will be asked to complete a 6-month follow up assessment via Qualtrics. The assessment is estimated to take 60 minutes to complete, and participants will be compensated \$30 for their time.
- b. Cortisol genetic testing kits and STI/HIV self-tests will be mailed out to participants post-intervention. Participants will be compensated \$20 for each completed test (\$40 total).

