MBQR is designed to alleviate the burden of minority stress and mental health and promote HIV testing and healthy sex behaviors among young adult gay men, bisexual men, queer men, and non-binary people assigned male at birth. Principles of MBQR include (a) reducing minority stress as a key theoretical guide, (b) affirming LGBTQ + identity and facilitating healthy identity development, (c) attending to intersectionality, (d) facilitating resilience and self-empowerment, (e) trauma sensitivity, and (f) promoting healthy relationships and a healthy community. Key techniques include through attention regulation to facilitate agency and self-awareness, enhancing emotion regulation, reducing reactivity to minority stress-informed thoughts, self-compassion to increase self-acceptance, and reducing behavioral avoidance. Formal and informal mindfulness practices will be offered, such as mindful walking, body scan, attention practice, self-compassion, etc. In addition to the 10 weekly sessions there is an all-day retreat (6hrs) that takes place around week 5. The participants also meet one-on-one with the instructor at the beginning and middle of class for a 30-minute welcome call and check in.

Health Education Active Control:

The online Health Education course, used as an active control in the RCT, is a self-paced program that can be largely completed independently (no group meeting, no all-day) by control group participants. The ten weekly modules are estimated to take 30 to 90 minutes each to complete and consist of readings, videos, infographics, and other related activities (e.g., reflections, quizzes).

The purpose of the health education course is to provide participants with general information on health, factors that affect health, and to promote health behaviors. Topics include sleep, exercise, healthy eating and body image, time management, alcohol and substance use, sexual health, school/work life balance, and healthy relationships. This information is provided without an emphasis on mindfulness.

Mindfulness-Based Queer Resilience (MBQR)-hybrid:

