Meditation-related risks: The National Center for Complementary and Integrative Health (NCCIH) states that meditation is generally safe for healthy people, but that adverse effects have also been reported.³⁴ Undesirable side effects and risks of meditation have been documented in more than 40 scientific reports [for reviews see³⁵⁻³⁷] and are listed in the Mindfulness-Based Intervention Guidelines.^{38,39} More common, less serious side effects that have been reported by individuals within the context of MBIs or of individuals who are meditating less than an hour per day include: increased depression, anxiety or panic, re-experiencing of traumatic memories, dissociation, executive dysfunction, headaches/body pain and insomnia.^{35,40-45} A few case reports of more serious side effects including mania, psychosis, and suicidality have been reported, mostly in the contexts of intensive retreats (>5 hrs/day) or in conjunction with pre-existing psychopathology.^{35,37,38,46} The frequency of serious adverse effects in the context of MBIs is estimated to be less than 1%, although adequate estimates are not available.⁴⁷

A number of actions have been taken to minimize meditation-related risks at different stages of the study. During the pre-enrollment stage, individuals with severe mental illness that could preclude regular class attendance or impact group participation (i.e., symptomatic, untreated bipolar disorder or a history of psychosis and/or schizophrenia) are excluded from the study and all risks are clearly communicated in the consent form. During treatment, meditations are relatively short and interspersed with dyads and reflections. Mindfulness homework assigned as part of the intervention is optional and is recommended to not exceed 1 hour per day. Teachers query participants about their experiences with meditation, and provide corrective feedback or modifications when needed. Developing strategies for working with physical and emotional discomfort is an explicit goal of the program. Because not all participants feel comfortable disclosing difficulties in class, an online “safety check-in” questionnaire will query meditation-related risks.

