Mindfulness-based Queer Resilience (MBQR) to Promote Mental and Sexual Health among Sexual and Gender Minority Young Adults: Statistical Analysis Plan

A mixed-methods approach will be used to understand feasibility and acceptability of this randomized controlled trial. Descriptive statistics will be used to summarize feasibility and acceptability measures from the full sample. These measures include recruitment rates, retention/attrition rates, session attendance, Client Satisfaction Questionnaire, and session evaluation form.

In addition, qualitative data from exit interviews will be analyzed using template analysis, a thematic analysis methodology that applies data reduction techniques for rapid turnaround, often used in intervention development and refinement research.

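### Apart from weekly PHQ-9/GAD-7, harms are not shown to be ascertained equally in both arms, and the SAP plans no harms summary

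*Protocol*

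**What the plan says.** **Harm-specific questions.** Under Meditation-related risks (Protocol section 6, Risks and Benefits), "Teachers query participants about their experiences with meditation". The next route is introduced with "Because not all participants feel comfortable disclosing difficulties in class", and the online safety check-in that follows "questionnaire will query meditation-related risks". No instrument, schedule, recipients or threshold for action is given.

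**Symptoms of concern.** The same section lists seven more common side effects: depression, anxiety or panic, re-experiencing of trauma, dissociation, executive dysfunction, headache or body pain, and insomnia.

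**Routine monitoring.** The weekly assessments (section 4) cover sexual risk, "monitoring of depression (PHQ-9) and anxiety symptoms (GAD-7"), and practice time. The safety check-in is not among these components.

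**General adverse events.** Safety Monitoring (section 6) covers serious, significant, unexpected and expected events without restriction by arm. Events are documented by staff, and participants receive contact details so that they can report between visits. No standard question set is described.

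**Contact by arm.** MBQR has weekly live classes, a retreat and two individual half-hour calls with the instructor (section 5), plus an exit interview (section 4). The control course is self-paced, largely done alone and has no group sessions (section 5).

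**Analysis.** The SAP summarises feasibility and acceptability descriptively: "These measures include recruitment rates, retention/attrition rates, session attendance, Client Satisfaction Questionnaire, and session evaluation form". It adds a qualitative analysis of exit interviews. Adverse events, the check-in and symptom worsening do not appear.

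**The concern.** A harm that is asked about in one arm and left to be volunteered in the other will be counted more completely in the first. Here the harm-specific questions are framed around meditation, which only MBQR delivers, so a control participant with new insomnia or dissociation has no described prompt to report it.

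This matters more than usual because participants must endorse distress on the PHQ-9 and GAD-7 to enter (section 3). The listed symptoms are plausible background complaints in such a sample. An MBQR-only count could not be separated from that background, and a by-arm count could make MBQR look worse than it is.

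The pilot is meant to inform later evaluation of the intervention, and the protocol itself concedes that the frequency of serious effects is not adequately estimated. Comparable by-arm harms data are something a randomised pilot with an active control can supply. As planned, even the data it does collect have no stated output.

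**Working it through.** The documents give no sample size, power or error rate for harms, so there is no figure of the plan's own to reproduce. The check is mainly a comparison of texts, with three short calculations.

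**1. Do controls receive the weekly PHQ-9/GAD-7?** Section 4 sends the weekly assessments to participants without naming an arm. The Compensation table can confirm this.
- Control: T1 40 + weekly 50 + T2 without exit interview 70 + T3 70 + optional hybrid-course assessment 30 + its exit interview 40 = 300, the stated total. Without the weekly 50 it would be 250.
- Intervention: 40 + 50 + 110 + 70 + 70 = 340, the stated total.

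So both arms are scheduled for the weekly scales.

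**2. Which listed side effects have a described, equal route in both arms?**

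| Listed side effect | MBQR | Control |
|---|---|---|
| Depression | weekly PHQ-9; teacher query; check-in | weekly PHQ-9 |
| Anxiety or panic | weekly GAD-7; teacher query; check-in | weekly GAD-7 |
| Re-experiencing, dissociation, executive dysfunction, pain, insomnia | teacher query; check-in | participant contact or staff documentation |

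Two of seven entries are actively measured on one schedule in both arms; five are not shown to be. Placing the check-in in the MBQR column is an inference from its wording, not a stated fact.

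**3. Direction of any bias.** Let p be the true proportion with a symptom, the same in both arms, and let c_M and c_C be the proportions of those cases that are captured. The expected apparent difference is p × c_M − p × c_C = p × (c_M − c_C). It is zero if capture is equal and counts against MBQR if c_M exceeds c_C. The documents give neither p nor c, so the sign can be argued but the size cannot be stated.

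**4. Length of observation.** Intervention participants are followed for about 12 months. Controls are followed for about 6, before an optional course that exposes them to mindfulness. If events occurred at one constant rate and were recorded throughout, raw counts over all follow-up would differ by a factor of 12/6 = 2 with no true difference. A by-arm table therefore has to stop at the 6-month follow-up.

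**5. What a by-arm table could show at the planned maximum of 30 per arm.**
- Zero events in 30: one-sided 95% upper limit = 1 − 0.05^(1/30) = 9.5% (two-sided exact limit 1 − 0.025^(1/30) = 11.6%).
- With a true serious-event rate of 1%, the chance of seeing at least one in 30 = 1 − 0.99^30 = 26%.
- Assumed rates of 10% v 20%: difference 10 points, standard error √(0.10×0.90/30 + 0.20×0.80/30) = 0.091, 95% interval −7.9 to 27.9 points.
- Power at an assumed two-sided 0.05: 19% for 10% v 20%, 49% for 10% v 30%, 78% for 10% v 40%.

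The table would be descriptive. It could not confirm the protocol's figure of below 1% for serious effects.

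**The case against.** The strongest reply is that the plan already monitors harm in both arms. Weekly PHQ-9 and GAD-7 measure the first two entries on the side-effect list on one schedule, and adverse-event monitoring is study-wide. This stands for depression and anxiety: there the gap lies only in the SAP. It does not answer the other five entries. The documents do not reproduce the items of either scale; if any item overlaps with, say, sleep, the gap is narrower for that symptom.

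Second, the recipients of the check-in are not stated, and the survey content sits in a separate Assessment document. An adverse-event item there cannot be excluded. This also stands, and is why the point is that equal ascertainment is not shown, rather than that it is absent.

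Third, the individual calls and the exit interview are not described as asking about harms. That is correct; they are extra occasions for disclosure, not planned harm queries.

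Fourth, with 30 per arm the comparison has little power. True, but the purpose is interpretable description, and the data cost almost nothing.

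A reader might infer stronger claims that the documents do not support:
- *Harms are asked about only in class.* The check-in is explicitly a route outside class.
- *The trial cannot compare harms.* Mood worsening can be compared from data already collected.
- *Controls have no contact.* They receive weekly surveys, later assessments and contact details.
- *The retreat falls in the protocol's own risk zone.* The protocol places serious effects "mostly in the contexts of intensive retreats (>5 hrs/day") or alongside existing psychopathology, and section 5 says "In addition to the 10 weekly sessions there is an all-day retreat (6hrs) that takes place around week 5". The six hours are the retreat's whole length, and the protocol describes its meditations as short and broken up by other activities. The point does not rest on this.

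**Conclusion.** The point holds in a limited form. Following the documents as written, five of the seven listed common side effects would have no demonstrably comparable control-arm rate, a raw count of them could be biased against MBQR, and no harms result of any kind is planned in the SAP.

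This rests on two assumptions: that the check-in goes to MBQR only, as its wording suggests, and that the separate Assessment document holds no neutral adverse-event items for both arms. If either is wrong, the ascertainment gap shrinks or closes; the SAP gap remains. It would be tempting to attach a percentage to the false excess, but any such figure would come from assumed capture rates for which the documents offer no basis.

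This is a worthwhile, inexpensive improvement. It is not a flaw that undermines the feasibility and acceptability aims.

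**What to change.** **Data collection.** Add the same few items to the weekly Qualtrics survey that both arms already receive, and to the post-intervention (T2) and 6-month (T3) surveys. Ask about new or worse symptoms from the protocol's own list, without mentioning meditation. State the recipients, instrument and schedule of the safety check-in.

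**SAP.** Add one descriptive by-arm table with confidence intervals, covering:
- adverse events, serious events and events leading to drop-out;
- responses to the common symptom items;
- PHQ-9 and GAD-7 worsening from baseline, with the baseline measurement and the definition of worsening fixed in advance.

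Limit it to the common period through the 6-month follow-up, and give the number of surveys returned per arm so that unequal response is visible. Put events reported through teachers or exit interviews in a separate MBQR-only listing, outside the by-arm counts.

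**Cost.** A few survey items and one SAP table; no new staff or visits. Surveys become slightly longer, more events will be recorded among controls, and intervals will be wide at 30 per arm, so the SAP should say that the table supports no formal safety conclusion.

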Aim 3. Examine the feasibility and acceptability of the internet-delivered mindfulness-based intervention (iMBI), called “Mindfulness-based Queer Resilience (MBQR)”, for HIV prevention. We will enroll and randomize a sample of 60 distressed, high-risk YMSM into one of two groups: MBQR intervention ($n=30$) or active control condition ($n=30$). We will aim to over enroll YMSM of color (e.g., Black/Latinx YMSM) and anticipate the group to include **approximately 50-60% Black/Latinx YMSM (or YMSM of color)**. Primary outcomes are **HIV and STI testing** and self-reported sexual risk behaviors. Secondary outcomes are stress biomarker (fingernail cortisol levels), psychological health, minority stress and coping. The study will examine recruitment and retention, number of sessions attended, self-reported at-home practice of mindfulness, completion of assessment, and acceptability of the intervention.

2. Aim 3 Study Design Overview

[figure not shown]
The methodological approach includes a 2-arm trial of MBQR vs. a *health education* control group, with up to $n=30$ per arm (total Aim 3 sample size = up to 60 participants enrolled and randomized). The study is intended to evaluate the impacts of MBQR on the outcomes outlined in the Specific Aims above.

All research assessments will take place digitally using Qualtrics, LLC (Provo, UT, USA) survey management tool. Participants will be sent secure links via email and SMS that can be accessed with their participant identification number. The MBQR intervention classes will be offered online via Zoom by a trained and qualified mindfulness instructor.

Baseline assessment links will be sent to all enrolled participants and completed prior to the start of the interventions. Follow up assessments will be conducted at three time points (post-intervention, 6-months follow up, and at 1-year follow up (for intervention participants only)).

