4. Steps in Recruitment, Screening, and Assessment:

Recruitment Timeline and Procedures

- 1) Timeline for recruitment:
 - a. Recruitment efforts will commence 2-4 months prior to the start of each study intervention.
 - b. Enrollment for each round will end on the date of the run-in session. Any individuals screened for the study after that date will be deferred to the next round (if applicable).
 - c. All preparatory efforts to be ready at least 8 weeks prior to the RCT
 - d. Participants will be recruited and enrolled into cohorts based on intervention scheduling. We anticipate enrolling around 8-10 participants

into each intervention and control group (e.g., we anticipate running two summer cohorts and one fall cohort).

- 2) Multi-Pronged Recruitment Strategy: Recruitment will be conducted primarily through four methods:
 - a. Community Advisory Board (CAB) member social networks – IRB approved recruitment materials will be provided to CAB members to distribute to their social networks and for them to post on their social media accounts.
 - b. Online social media (e.g., Facebook-based community groups for gay and bisexual men, Reddit threads, Twitter, etc.)
 - c. Emails to University/College campus groups, Community-based Organizations, and partner health groups (e.g., the Fenway Institute in Boston)
 - d. Targeted recruitment through BuildClinical® - see separate BuildClinical® recruitment proposal

Screening Procedures: Participants will be screened for eligibility in three steps.

- 1) Online Screening Form - First, individuals interested in the study, will be prompted to complete a brief (5-15 minute) internet-based screening form via Qualtrics to determine their initial eligibility. Individuals who screen eligible will then be redirected to a separate Qualtrics form where they can review the Informed Consent Form (ICF) and complete a contact form for follow-up.

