Baseline Procedures, Enrollment, Run-In, and Randomization

- 1) Baseline Procedures:
 - a. Eligible participants will be asked to complete a baseline survey via Qualtrics that is estimated to take 60-80 minutes to complete (see separate Assessment document for details).
 - b. At baseline they will also be mailed a Cortisol genetic testing kit that will provide them with the necessary equipment to collect a baseline nail sample (see separate cortisol nail sampling protocol for details). Participants will then mail back the completed sample back to the study staff for further processing. Participants will be compensated \$20 for each genetic sample provided.
 - c. Following baseline survey completion, participants are considered as "enrolled and ready to be randomized".
- 2) Run-in Session: Prior to randomization participants will be asked to attend a mandatory 30-minute introduction session via Zoom that will serve as a 'run-in' session for individuals interested in the study. The purpose of this session will be to:
 - a. Provide a brief overview of the randomization process and intervention arms. This includes an emphasis on the time commitment required for the interventions and for the study as a whole.
 - b. Introduce the research team and the course interventionists.

- c. Walk through the HIV/STI self testing and genetic cortisol sampling procedures; remind participants to mail in their samples / submit their results.
- d. Answer any questions.
- e. Allow participants an opportunity to opt out of the study (submitted privately by email, phone, text, etc.) prior to the randomization. Note that participants can withdraw at any time. The run-in session allows participants an additional opportunity to opt out prior to being included in the randomization. This helps with overall group balance and retention.
- f. Participants who complete the baseline assessment and opt in to the study following the run-in session will be included in the randomization; they will be coded as “enrolled and randomized”.

3) Randomization:

- a. Prior to intervention commencement, participants will be randomly assigned to one of two groups: (1) MBQR Intervention group; or (2) a health education control group.
- b. Control group participants who complete the study will be given the opportunity to participate in the intervention (MBQR-hybrid) after the 6-month follow up assessments are completed.

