Fidelity Monitoring: Intervention fidelity will be ensured by (1) rigorous, program specific training for the instructor with feedback (2) recording of all sessions with a 10% quality audit reviewed with instructor after each cohort (3) monitoring participant attendance, home practice of treatment skills, and understanding of skills (see Feasibility) (4) a comprehensive mixed methods approach (e.g. practice logs) for understanding of treatment enactment. In assessing MBQR Instructor competency and treatment fidelity, a randomly selected 10% or more of the recorded sessions will be reviewed by trained research assistants and rated for proportion of adherence to the MBQR curriculum guide. Intervention integrity for MBQR will be assessed using the Mindfulness-Based Interventions-Teaching Assessment Criteria (MBC-TAC), which is the most respected quantitative approach world-wide for assessing mindfulness-based programs. In order for the MBQR intervention and its associated data to be included in the sample, the instructor needs to demonstrate 90% or greater curriculum adherence.

Protocol Deviations:

Protocol deviations will be reported to the Brown University IRB. A description of the deviations, and any effects on the protection of human subjects will be documented. Investigator(s) will review protocol deviations and determine on a case by case base which data (if any) will be excluded from the final data set.

Participant Rights and Confidentiality

Institutional Review Board

The protocol, the informed consent document, and any subsequent modifications, will be reviewed and approved by the Brown University IRB responsible for oversight of the study.

Informed Consent Documents

Prior to enrollment, all participants will be provided with an IRB-approved Informed Consent document. The consent form will describe the purpose of the study, the procedures to be followed, and the risks and benefits of participation. Informed consent is an ongoing process. Participants will first be presented with the Informed Consent Form (ICF) at the time of initial online screening. They will have the option to download and save the ICF and will also be prompted to click through the ICF text in full (displayed on multiple screens in Qualtrics). The consent process will continue into the Zoom Interviews #1 and #2, where a trained research staff member will review the ICF with the participant and answer any questions they might have.

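### MBQR data count only if the instructor reaches 90% curriculum adherence, a condition judged after randomisation and in one arm only, and the SAP does not set it aside

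*Protocol*

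**What the plan says.** Protocol section 6, under Quality Assurance (Fidelity Monitoring), sets a condition on data: for "MBQR intervention and its associated data to be included in the sample, the instructor needs to demonstrate 90% or greater curriculum adherence". The same paragraph has research assistants rate a random sample of at least 10% of the session recordings, and has the audit discussed with the instructor once each cohort is finished.

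Protocol section 4 (Randomization) fixes the order of events: "Prior to intervention commencement, participants will be randomly assigned to one of two groups". Section 5 describes the control course, which "is a self-paced program that can be largely completed independently (no group meeting, no all-day) by control group participants". No adherence condition is stated for that arm.

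On numbers, the Aim 3 design overview gives "total Aim 3 sample size = up to 60 participants enrolled and randomized", with up to 30 per arm. The recruitment timeline in section 4 says "We anticipate enrolling around 8-10 participants" into each intervention and control group and, as an example, "we anticipate running two summer cohorts and one fall cohort".

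The SAP says: "Descriptive statistics will be used to summarize feasibility and acceptability measures from the full sample". It lists recruitment, retention, session attendance, a satisfaction questionnaire and a session evaluation form. It does not define the sample and does not refer to the adherence rule.

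**The concern.** The rule is worded as a condition for entering the sample, not as a training target. It depends on something that happens after randomisation, and it can act on one arm only. A participant randomised to MBQR who attended every session could be left out because of the instructor's score. No control can be left out by this rule.

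Aim 3 is about feasibility and acceptability, and whether instructors can deliver the course to standard is itself a feasibility result. If courses below the target are removed, retention, attendance and satisfaction no longer describe everyone assigned to MBQR. The design overview also states a wider purpose: "The study is intended to evaluate the impacts of MBQR on the outcomes outlined in the Specific Aims above". Any such evaluation would lose the comparison as randomised.

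**Working it through.** **Timing.** Participants are assigned before the courses begin. Adherence is rated on recordings of the sessions. A session cannot be recorded before the course starts, so the rating follows randomisation.

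**Which text prevails.** The design overview counts its sample as those enrolled and randomised, so *full sample* in the SAP most naturally means the same people. On that reading the SAP and the fidelity rule conflict. If the fidelity rule instead decides who is in the sample, the SAP inherits the exclusion. Neither document says which applies.

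**Planned arm size.** Three cohorts of 10 give 3 × 10 = 30, which matches the stated 30 per arm. Three cohorts of 8 give 3 × 8 = 24.

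**Share of the MBQR arm at risk.** Assume exclusion by cohort and three cohorts of sizes a, b and c, each 8, 9 or 10. With the first cohort lost, the share is a/(a+b+c).

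- One lost, minimum: 8/(8+10+10) = 8/28 = 28.6%, leaving 20.
- One lost, equal cohorts of 10: 10/30 = 33.3%, leaving 20 MBQR against 30 controls.
- One lost, maximum: 10/(10+8+8) = 10/26 = 38.5%, leaving 16.
- Two lost, minimum: (8+8)/(8+8+10) = 16/26 = 61.5%, leaving 10.
- Two lost, maximum: (10+10)/(10+10+8) = 20/28 = 71.4%, leaving 8.

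The two-cohort figures also apply if the rule works per instructor and a failing instructor taught two of the three cohorts. The documents do not allocate cohorts to instructors, so that is an assumption.

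**Precision of a between-arm comparison, if one were made.** With equal standard deviations, 20 against 30 instead of 30 against 30 multiplies the standard error of a mean difference by √[(1/20 + 1/30)/(2/30)] = √1.25 = 1.12.

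**How much data the pass or fail could rest on.** Ten per cent of ten weekly sessions is 1 session per cohort. If the retreat counts as an eleventh session, 10% is 1.1, or 2 after rounding up. The protocol allows more than 10%, so these are minimums.

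**The case against.** The strongest reply is that the rule may never be triggered. Instructors must be qualified or certified mindfulness teachers, or doctoral-level psychologists or licensed professionals, and they receive 20 to 30 hours of training with feedback. That bears on how likely exclusion is, but it does not remove the rule.

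The SAP plans descriptive and qualitative work with no between-arm comparison. This stands, and it limits the present effect to the MBQR feasibility and acceptability summaries. Recruitment rates are untouched. The loss of the as-randomised comparison matters only for the stated purpose of evaluating impacts, for which the SAP gives no analysis. A self-paced course would not be expected to have an instructor score, so the missing control rule is no oversight in itself. The difficulty is using a one-arm score to decide whose data count.

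The percentages are conditional, and that also stands. Three cohorts is an example, 8 to 10 is approximate, and the unit of exclusion is unstated. The audit's timing points towards the cohort, but the rule itself names the instructor.

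Three stronger readings are tempting and are not supported:

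- A reader might infer that the whole arm is at risk. That would need exclusion per instructor and one person teaching every cohort. The protocol's opening list has two teacher entries, one still to be announced, and its training text allows for more than one instructor.
- A reader might infer that the exclusions would flatter MBQR. The documents give no link between adherence and outcome. If there is none, there is no bias.
- A reader might see a contradiction with the section on withdrawal during the intervention, which keeps inviting people who stop their course to follow-up. That section governs data collection and the fidelity rule governs inclusion, so both can hold.

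**Conclusion.** The concern holds in a limited form. The protocol makes inclusion of MBQR data depend on a score obtained after randomisation, in one arm, with no stated unit. The SAP's undefined *full sample* leaves this unresolved. It should be fixed before the data are summarised.

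Under the illustrative assumptions of three cohorts and exclusion by cohort, one failure removes about a third of the MBQR arm (28.6% to 38.5%). More could go if the rule works per instructor. The chance of triggering the rule, and the size and direction of any bias, cannot be derived from the documents.

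**What to change.** - Delete the 90% score as a condition for inclusion in the main analysis.
- State in the SAP that retention, satisfaction and outcomes are summarised for all randomised participants in their assigned arm, regardless of instructor adherence.
- Summarise MBQR session attendance and session evaluations for all randomised to MBQR, again regardless of adherence.
- Give recruitment rates their own denominator of people screened or eligible. Defining *full sample* simply as all randomised would not suit them, although the SAP lists them under that term.
- Report instructor adherence as a fidelity and feasibility result. Use the 90% threshold only in a pre-specified sensitivity summary that states its unit.

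The cost is wording in the protocol and SAP. The downside is that poorly delivered courses stay in the main summaries, so the MBQR figures may move in either direction.

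A separate, secondary point is that the Protocol Deviations paragraph allows case-by-case exclusion of data in either arm, without criteria or timing. Those decisions should be made before outcomes by arm are seen, and listed by arm.
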